- 2) To allow a physical examination completed by the Principal Investigator or his/her designee on a newly diagnosed study participant prior to the participant signing study consent to be utilized as the physical examination currently required at study baseline screening visit 1. This physical examination and associated urine and/or EPS lab results, conducted up to four (4) weeks prior to study baseline screening visit #1, will be acceptable for satisfying screening visit requirements. A focused physical examination is part of the routine standard of care in the initial evaluation of a urology patient and therefore, will reduce participant burden and inconvenience in not having multiple identical procedures performed within a short period of time.
- 3) To clarify that all sites do not need to use the same brand of dipstick for urinalysis.
- 4) To clarify sample size adjustments and the frequency of Patient Recruitment reports.

2. TRIAL TESTS AND PROCEDURES

• Current Protocol Text Reads:

[Section 7.2 Screening Visit#1 – item #6] *Physical Examination*. Each participant will undergo a focused physical examination. This examination will include an abdominal exam, external genital exam, rectal exam, prostate exam, and perineal exam.

Change Protocol Text to Read:

[Section 7.2 Screening Visit#1 – item #6] *Physical Examination*. Each participant will undergo a focused physical examination at this baseline visit. This examination will include an abdominal exam, external genital exam, rectal exam, prostate exam, and perineal exam. If the participant has received a prior focused physical examination conducted by the Principal Investigator or his/her designee within four (4) weeks of study enrollment, a documented copy of this prior physical examination will be acceptable.

• Current Protocol Text Reads:

[Section 7.2 Screening Visit#1 – item #7] *Urinalysis, Urine, and EPS Specimens for Microscopy and Culture.* Each participant will provide two (2) urine specimens (VB2 and VB3) and an EPS (expressed prostatic secretion) specimen for either analysis or culture.

Change Protocol Text to Read:

[Section 7.2 Screening Visit#1 – item #7] *Urinalysis, Urine, and EPS Specimens for Microscopy and Culture*. Each participant will provide a VB2 specimen, a VB3 and/or EPS (expressed prostatic secretion) specimen for either analysis or culture. If the participant has provided these specimens as part of the focused physical examination conducted by the Principal Investigator or his/her designee within four (4) weeks of study enrollment, a documented copy of these laboratory results will be acceptable.

• Current Protocol Text Reads:

[Section 7.2 Screening Visit#1 – item #7] *Urinalysis, Urine, and EPS Specimens for Microscopy and Culture*. Dipstick urinalysis will be conducted on the midstream urine (VB2) for macroscopic analysis; all centers will be required to use the same brand of dipstick.

The statement "all centers will be required to use the same brand of dipstick" has been removed.

3. STATISTICAL CONSIDERATIONS

• Current Protocol Text Reads:

[Section 10.2 Sample Size Calculations] "This proposed sample size includes adjustments for clustering within clinical sites (5% increase), withdrawal (15% increase), and interim monitoring (5% increase)"

Change Protocol Text to Read:

[Section 10.2 Sample Size Calculations] "This proposed sample size includes adjustments for clustering within clinical sites (20% increase) and interim monitoring (5% increase)".

• [Section 10.6 Report Table]

Frequency of Patient Recruitment/Targets Report changed from "q2 weeks" to "q4 weeks".

Clinical Research Computing Unit (CRCU)

Department of Biostatistics and Epidemiology

CPCRN-2 RCT #1(Alfuzosin Trial) protocol AMENDMENT #2

Introduction:

The Chronic Prostatitis Collaborative Research Network 2 (CPCRN-2) Clinical Trial Protocol #1 entitled: "A Randomized Multicenter Double-Blind Clinical Trial to Evaluate the Efficacy and Safety of 10mg Alfuzosin in the Treatment of Chronic Prostatitis / Chronic Pelvic Pain Syndrome (CP/CPPS) in Recently-Diagnosed and/or Newly-Symptomatic Alpha-blocker Naïve Patients"- Version 1.0 – Effective August 16, 2004, was developed by the CPCRN-2, and will be maintained by the Data Coordinating Center (DCC) at the University of Pennsylvania over the course of the study through issuance of protocol amendments and revisions.

The first edition of this protocol (Version 1.0, August 16, 2004) is being amended as of the effective date July 20, 2005. Please refer to the protocol table of contents for the location of changes listed below.

Summary of Protocol Amendment #2

- 1. Revise entry criteria to remove "chronic" epididymitis from the list of symptoms in Deferral Criteria #4 and to remove Deferral Criteria #6 to reflect a label change allowing the use of erectile dysfunction medications with alpha blockers.
- 2. Allow prospective participants to return for their Screening Visit #2 when their 2-day urine culture results (required to assess eligibility) are available, rather than wait at least 7 days to return.

1. PARTICIPANT CRITERIA

- **a.** [Section 4.1.3 Deferral Criteria #4] Participant has experienced symptoms of acute or chronic epididymitis within the past three (3) months.
- *Change Protocol Text to Read*: Participant has experienced symptoms of acute epididymitis within the past three (3) months.
 - **b.** [Section 4.1.3 Deferral Criteria #6] Participant has been taking excluded medications such as Cialis®, Levitra®, and Viagra® in the past one (1) week.
- Remove this deferral criteria

2. TRIAL TESTS AND PROCEDURES

- **a.** [Section 7.1 Procedural Summary- second paragraph] This study is comprised of phases for each participant: i) the screening phase and ii) the treatment and follow-up phase. The screening phase, which assesses a participant's eligibility via inclusion, exclusion, and deferral criteria, will consist of two baseline visits no more than four (4) weeks and no less than one (1) week apart.
- Change Protocol Text to Read: This study is comprised of phases for each participant: i) the screening phase and ii) the treatment and follow-up phase. The screening phase, which assesses a participant's eligibility via inclusion, exclusion, and deferral criteria, will consist of two baseline visits no more than four (4) weeks and no less than two (2) days apart (when 2-day urine culture results are available).

- **b.** [Section 7.2 Screening Visit#1 first sentence] The first screening visit should occur no more than four (4) weeks and no less than one (1) week prior to randomization.
- Change Protocol Text to Read: The first screening visit should occur no more than four (4) weeks and no less than two (2) days prior (when 2-day urine culture results are available) to randomization.
 - **c.** [Section 7.3 Screening Visit#2 first sentence] Screening Visit #2 should be completed at least one (1) week after, but no more than four (4) weeks after Screening Visit #1.
- Change Protocol Text to Read: Screening Visit #2 should be completed at least two (2) days after (when 2-day urine culture results are available), but no more than four (4) weeks after Screening Visit #1.

Table of Contents

1	Introduction	1
2	STUDY DESIGN AND OBJECTIVES 2.1 Primary Objectives 2.2 Secondary Objectives 2.3 Study Design 2.4 Study Time Frame 2.5 Study Organizations 2.6 Study Endpoints 2.6.1 Primary Endpoint 2.6.2 Secondary Endpoints	1 2 2 2 3
3	STUDY INTERVENTIONS AND RATIONALE 3.1 Alfuzosin (Uroxatral®)	4
4	Participant Criteria 4.1 Study Population 4.1.1 Inclusion Criteria 4.1.2 Exclusion Criteria 4.1.3 Deferral Criteria	6 7
5	PARTICIPANT RECRUITMENT AND CONSENT. 5.1 Participant Recruitment 5.2 Informed Consent. 5.2.1 HIPAA Authorization. 5.2.2 Patient Confidentiality. 5.3 Risks and Benefits to Participants. 5.3.1 Risks of Alfuzosin (Uroxatral®) 5.3.2 Risks of Placebo.	

	10.6.1 Final Analysis	
	10.6.2 Statistical Computing	23
11	REFERENCE LIST	24
APPI	ENDIX A: FORMS AND VISIT SCHEDULE	28
APPI	ENDIX B: PROPOSED INFORMED CONSENT FORM	29
APPI	ENDIX C: ADDITIONAL DETAILS OF STUDY AGENT	35
APPE	ENDIX D: LABORATORY METHODS	42

1 Introduction

Nonbacterial prostatitis, also referred to as prostatodynia, chronic prostatitis (CP), and chronic pelvic pain syndrome (CPPS), is a diagnosis applied to men experiencing pelvic (perineal, testicular, penile, lower abdominal) pain, with or without voiding symptoms, in the absence of a specific identifiable symptom cause. Despite its high prevalence (5%-16%), 2-4 surprisingly little is certain about the etiology, diagnosis, and effective treatment of this syndrome. The symptoms may or may not be associated with the prostate gland. Standard diagnostic tests and evidence-based treatments are lacking. 5.6 Therapy is usually with antibiotic medications, despite negative culture findings and no randomized clinical trial evidence to support this choice of treatment.

Chronic prostatitis is a significant cause of health care use. The syndrome accounts for about two million office visits per year in the United States, and many patients undergo multiple, diverse diagnostic procedures and treatments. Analysis of National Ambulatory Medical Care Surveys of 1990-1996 revealed that visits associated with a diagnosis of prostatitis were approximately equally divided between urologists and primary care physicians offices. 8;10

Non-bacterial prostatitis or chronic prostatitis/chronic pelvic pain syndrome (CP/CPPS) is a condition affecting men, characterized by idiopathic pelvic pain with or without urinary symptoms. Although symptoms of urinary frequency and urgency may be present in some patients with prostatitis, in general, it is the absence of these urologic symptoms that diagnostically differentiates this syndrome from Interstitial Cystitis (IC), which is found in both men and women. Urodynamic and endoscopic abnormalities are found both in IC and CP/CPPS. Algorithms are characterized by inflammation in genitourinary (GU) secretions (Type IIIA) or absence of genitourinary inflammation (Type IIIB). Asymptomatic chronic inflammatory prostatitis (Type IV) is detected in some men evaluated for infertility or prostate cancer. The relationship to CP/CPPS (Type III) is unknown. Infection with common GU pathogens is not present in either IIIA or IIIB although infection with organisms not detectable on culture cannot be eliminated. There is little evidence for an infectious etiology. Other possible etiologies are immunologic response, how musculoskeletal abnormalities, neuropathic inflammation, and genetic causes.

Findings from a recent CPCRN study revealed no significant treatment effect with ciprofloxacin or tamsulosin hydrochloride. Smaller studies, however, have shown positive treatment effect with the use of prolonged treatment with alpha-adrenergic blocking agents terazosin and alfuzosin in specific populations of patients early in the course of the disorder. Alfuzosin is a more recent alpha-adrenergic blocking agent and may affect both the peripheral and central nervous system response to pain. We believe there is enough evidence to study the treatment of alfuzosin in patients with relatively new onset CP/CPPS.

2 STUDY DESIGN AND OBJECTIVES

2.1 Primary Objectives

[figure not shown]
- 1. To compare 12 weeks of treatment with alfuzosin versus placebo in newly-diagnosed, alpha-blocker naïve CP/CPPS participants with respect to the primary endpoint in the NIH-CPSI.
- 2. To evaluate the safety and tolerability of 12 weeks of alfuzosin in newly-diagnosed, alpha-blocker naïve CP/CPPS participants.

2.2 Secondary Objectives

- 1. To characterize newly-diagnosed, alpha-blocker naïve CP/CPPS participants with respect to symptom severity.
- To assess the incidence of depression and anxiety, and its relationship to symptom severity and response to treatment, in newly-diagnosed, alpha-blocker naïve CP/CPPS participants.
- 3. To assess domains of male sexual function and its relationship to symptom severity and response to treatment, in newly-diagnosed, alpha-blocker naïve CP/CPPS participants.
- 4. To assess the impact of patient expectations on symptom severity and response to treatment, in newly-diagnosed, alpha-blocker naïve CP/CPPS participants.

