2.6.2 Secondary Endpoints

A number of secondary outcome measures related to both specific symptoms and overall symptom scores will be used to supplement the analysis based on the primary endpoint. One secondary endpoint will be a participant-reported Global Response Assessment (GRA) of symptom change at twelve (12) weeks relative to baseline or withdrawal; whichever comes first. Additional symptom-related secondary outcome measures include the subscales of the NIH-CPSI (for pain, urinary symptoms, and quality of life), the McGill Pain Questionnaire (a measure of pain intensity), the MOS SF-12 (a measure of health-related quality of life), the Hospital Anxiety and Depression Scale (a measure of depressive symptom severity), the International Index of Erectile Function (a measure of male sexual function), and select questions from the Male Sexual Health Questionnaire (for ejaculatory function and ejaculatory bother). When combined, the primary and secondary endpoints address all of the recommended core outcome domains for chronic pain clinical trials. Laboratory and procedural measures to be assessed at baseline include urine screening and expressed prostatic secretions (EPS) and urine testing.

Additional details of the proposed secondary endpoints are provided below.

- Symptom Assessment Form (SYM): These are individual questions about pain, urgency and abnormal frequency obtained on 0 10 Likert scales.
- Global Response Assessment (GRA): The GRA is a single question patient-driven symmetrical outcome scale with seven categories ranging from 1 for "markedly worse" to 4 for "no change" to 7 for "markedly improved". The GRA has been recommended as the primary outcome measure for interstitial cystitis (IC) trials²² and has been used as the primary outcome measure in two NIDDK sponsored studies in IC. This question will only be asked during follow-up visits.
- McGill Pain Questionnaire (MPQ): The MPQ will be used because it evaluates the quality of pain as well as the intensity of pain, adding a dimension that the NIH-CPSI does not capture. Total pain scores and both subscores of sensory and affective pain will be evaluated.
- Medical Outcomes Study Short Form 12 (SF-12): Both the Physical Composite Score (PCS) and the Mental Composite Score (MCS) will be evaluated
- Hospital Anxiety and Depression Scale (HADS)-This 14-question scale provides scores for the independent measures of anxiety and depression.

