7.2 Screening Visit #1 (First Baseline Screening Visit)

The first screening visit should occur no more than four (4) weeks and no less than two (2) days

prior (when 2-day urine culture results are available) to randomization. During this screening visit, the forms and procedures listed below will be completed. If a participant fails to meet any of the study eligibility criteria, based on the data collected during this visit, he would not be required to complete the physical examination, urinalysis, or urine culture for the purposes of the study.

Eligibility Criteria. Each participant will complete a preliminary screening form that checks whether he meets the initial inclusion/exclusion/deferral criteria. These criteria will be verified at the second baseline visit.

Participant Contact Information. Participants will be asked to provide the clinical center with their address, phone (home, work, and cell) number, e-mail address, primary care physician, and the name, telephone number, and address of two other contacts. This information will be stored at the Clinical Center and available only to selected study personnel.

Participant Medical History. Each participant will provide the research staff with general medical history and specific genitourinary medical history. In particular, the participant will be asked to provide information regarding his disease and surgical histories.

Demographic Questionnaire. Each participant will provide the research staff with his demographic information, including date of birth (age), race, ethnicity, marital status, income, and level of education.

Participant Symptom Index. Each participant will provide the research staff with an assessment of his discomfort/pain by completing the NIH-CPSI and also complete the three questions about pain, urgency, and frequency on the SYM form.

Physical Examination. Each participant will undergo a focused physical examination at this baseline visit. This examination will include an abdominal exam, external genital exam, rectal exam, prostate exam, and perineal exam. If the participant has received a prior focused physical examination conducted by the Principal Investigator or his/her designee within four (4) weeks of study enrollment, a documented copy of this prior physical examination will be acceptable.

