7.3 Screening Visit #2 (Second Baseline Screening Visit) and Randomization

Screening Visit #2 should be completed at least two (2) days after (when 2-day urine culture results are available), but no more than four (4) weeks after Screening Visit #1. Participants who still meet all eligibility criteria at this visit will complete the questionnaires described below, and will continue on to randomization. During this visit, the patient will have an opportunity to ask questions and express concerns related to the study.

Eligibility Checklist. An eligibility checklist confirming that the participant still meets all eligibility criteria will be completed by the RC prior to randomization.

Concomitant Medications. The research staff will record the medications currently being taken by the participant. Participants will be asked to recall their medications if they fail to bring them to the second screening visit.

Adverse Events/Serious Adverse Events. The research staff will record any adverse events that have newly occurred, changed, or have been resolved.

Urinalysis, Urine, and EPS Specimens for Microscopy and Culture. The research staff will review culture results from the baseline visit to determine participant eligibility.

Symptom Questionnaires. Each participant will complete the following symptom questionnaires at this visit and all subsequent follow-up visits:

- 1. NIH-Chronic Prostatitis Symptom Index (NIH-CPSI)
- 2. Symptom Assessment Form (SYM)
- 3. MOS SF-12 Health Status Questionnaire (SF-12)
- 4. McGill Pain Questionnaire (MPQ)
- 5. Hospital Anxiety and Depression Scale (HADS)
- 6. International Index of Erectile Function (IIEF)
- 7. Male Sexual Health Questionnaire (MSHQ)

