7.4.1 Week Six (6) Clinic Visit

Concomitant Medications. The research staff will record the medications currently being taken by the participant. Participants will be asked to recall their medications if they fail to bring them to the second screening visit.

Adverse Events/Serious Adverse Events. The research staff will record any adverse events that have newly occurred, changed, or have been resolved.

Symptom Questionnaires. As described in Section 7.3, the participant will be required to complete a number of different questionnaires, with the addition of the single question GRA, which is only completed during the week six (6) and week twelve (12) post-treatment visits.

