7.4.2 Week Twelve (12) Clinic Visit

At week twelve, participants will complete the same forms and questionnaires as the clinic visit at week six, with the addition of the following:

- 1. Study Stop Form
- 2. Treatment Stop Form

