10.5.3 Secondary Analyses

A number of secondary analyses will be conducted, both to evaluate the secondary symptom-related outcomes and to supplement the primary endpoint comparison. Secondary outcomes are listed in Section 2.5 and include the GRA, subscores of the NIH-CPSI, the MOS SF-12, the MPQ, the HADS, the IIEF, and the MSHQ.

For example, one type of response will be based on the participant GRA of change as measured at twelve (12) weeks or withdrawal, whichever comes first. One method of analysis will be to classify participants who indicate that they are "moderately or "markedly" improved as intervention responders. The analysis of this binary outcome will be identical to that described for the primary endpoint above. Additional analysis examining the correlation between a 6-point decrease and/or a 25% mean change in the NIH-CPSI could also be conducted, if needed to provide additional measures of responsiveness.

For the various measures evaluated repeatedly over time, changes over time will be compared among treatment groups using methods for longitudinal data analysis⁴⁸. These methods will include random effects regression models for continuous outcomes and GEE methods for categorical and ordinal outcomes such as the GRA⁴⁸. Both within- and between-participant variability in these outcomes will be carefully assessed to provide pilot data for future clinical trials. When applicable, additional analyses of the symptom outcomes may include evaluation of secondary response rates defined by specific changes in symptoms (i.e. 50% drop in symptom score). For measures obtained only at baseline and one follow-up time point, change from baseline will be compared among groups using analysis of variance (ANOVA) and regression methods. Withdrawal rates will be compared between arms using standard methods. Also, modeling the informative of dropout patterns may be conducted to address whether or not the extent of adherence at 12 weeks is associated with the level of treatment response.

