APPENDIX A: FORMS AND VISIT SCHEDULE

	-1 to -4 Weeks (Screening)	0 Weeks (Randomization)	6 Weeks (Follow-up)	12 Weeks (Follow-up)
Form Name	Visit 1 (B1 Clinic)	Visit 2 (B2 Clinic)	Visit 3 (Clinic)	Visit 4 (Clinic)
Prescreening/Screening/Baseline				
Pre-Screening Summary (PRESCR)				
Informed Consent (Administrative)	X			
Medical History (MEDHX)	Х			
Eligibility Checklist (ELIG)	Х	Χ		
NIH-Chronic Prostatitis Symptom Index (CPSI)	Х	Х	Χ	Χ
Randomization (RAND)		Х		
Procedures and Labs				
Adverse Events/Serious Adverse Events (AE)		Χ	Χ	Χ
Demographics (DEMO)	Χ			
Dispensing Log (DISP)		Χ	Χ	
Drug Compliance (DCOMP)			Χ	Χ
EPS and Urine Testing (EUT)	Χ			
Physical Exam (EXAM)	Х			
Urine Screening (URINE)	Х			
Symptom Questionnaires				
Symptom Assessment (SYM)	X	X	X (GRA)	X (GRA)
Health Status Questionnaire® (SF-12)		Χ	Χ	X
The McGill Pain Questionnaire® (MPQ)		Χ	Χ	Χ
Hospital Anxiety and Depression Scale® (HADS)		Χ	Χ	Χ
The International Index of Erectile Function® (IIEF)		Χ	Χ	X
The Male Sexual Health Questionnaire (MSHQ)		Х	X	X
PRN Forms				
Study Stop Point (SSTOP)	PRN	PRN	PRN	X
Treatment Stop Point (TSTOP)	PRN	PRN	PRN	X
Unmasking Record (UNMASK)	PRN	PRN	PRN	PRN
Administrative Forms				
Clinical Center Staff "Signature and Delegation of	Х	DDM	DDM	DDM
Responsibilities" Log (STAFFLOG)	X	PRN	PRN	PRN
Concomitant Medication (CMED)	Х	Х	Х	Х
Participant ID Assignment Log (PTLOG)	Х			
Participant Contact Information (PTCONT)	Х			
Participant Transfer (TRANS)	PRN	PRN	PRN	PRN
Study Drug Tracking Log (TRACK)		Х	Χ	
Visit Checklist	Х	X	Χ	X

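### Secondary objective 4 concerns patient expectations, but the protocol names no measure of expectation among its endpoints, visit procedures or forms

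*Protocol*

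**What the plan says.** Protocol section 2.2 gives four secondary objectives. The fourth is "To assess the impact of patient expectations on symptom severity and response to treatment", in the same newly diagnosed, alpha-blocker naïve population as the other three.

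The data to be collected are described in several places:

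- Section 2.6.2 lists the secondary endpoints: GRA, NIH-CPSI subscales, SYM, MPQ, SF-12, HADS, IIEF, selected MSHQ questions, specimens and adverse events.
- Section 7.2 (Screening Visit 1) collects history, demographics and the NIH-CPSI, and has the man "complete the three questions about pain, urgency, and frequency on the SYM form".
- Section 7.3 (Screening Visit 2 and randomisation) states: "Each participant will complete the following symptom questionnaires at this visit and all subsequent follow-up visits". Seven instruments follow by name: NIH-CPSI, SYM, SF-12, MPQ, HADS, IIEF and MSHQ.
- Section 7.4.1 (week 6) repeats these "with the addition of the single question GRA, which is only completed during the week six (6) and week twelve (12) post-treatment visits".
- Section 7.4.2 (week 12) says that "participants will complete the same forms and questionnaires as the clinic visit at week six", and adds two stop forms.
- Appendix A sets out the forms by visit. No row is titled as an expectation form.

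Sections 8.4 and 10.3 also plan to ask participants, at the end of their participation, which arm they think they were in. Section 10.3 asks the treating physicians as well. Both sections give the purpose as judging whether blinding held.

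**The concern.** An objective about the effect of expectation needs a recorded value of expectation for each man. That value should come from a time when his expectation cannot yet have been shaped by how he fared on study drug. If none is collected, the objective cannot be addressed from the trial's own data. The gap also cannot be closed later: a baseline attitude cannot be recovered once treatment has begun, and an analysis plan works only on data that exist.

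The question matters in this trial. The primary endpoint is built on a patient-reported score, and section 10.2 assumes that 40% of the placebo arm will respond. Expectation is a natural candidate for explaining part of that, and the network chose to make it a stated objective.

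**Working it through.** No arithmetic applies. The check traces each secondary objective in section 2.2 to the instruments named elsewhere in the protocol.

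| Secondary objective (2.2) | Variable needed | Named instrument (2.6.2, 7.2 to 7.4, Appendix A) |
|---|---|---|
| 1 | Symptom severity | NIH-CPSI, SYM, MPQ |
| 2 | Depression and anxiety | HADS |
| 3 | Male sexual function | IIEF, MSHQ |
| 4 | Patient expectations | None |

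The outcome side of objective 4 is covered, because severity and response come from the NIH-CPSI and the GRA. Only the explanatory side is missing.

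Next, could any listed item serve as an expectation measure under another name?

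- **Seven Visit 2 questionnaires.** As described in 2.6.2 and 7.3, they record current symptoms, pain, health status, mood and sexual function. None is described as asking what the man expects from treatment.
- **SYM.** Section 7.2 limits it to three questions, on pain, urgency and frequency.
- **GRA.** It rates change since baseline and is asked only at follow-up. It looks back at an outcome and does not record an expectation.
- **Medical history and demographics.** Section 7.2 describes these as general and genitourinary history, disease and surgical history, and personal characteristics.
- **Treatment guess (8.4, 10.3).** It asks about assignment, not expected benefit. By then the man has lived through any improvement and any side effects, so his guess may be a consequence of response. It cannot show an effect of expectation on response, and it says nothing about expectation and severity at entry.

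Patient expectations are mentioned only in section 2.2. Elsewhere the protocol uses the idea of expecting for accrual, withdrawal and adverse events. Section 10.5.3 says the secondary outcomes "include the GRA, subscores of the NIH-CPSI, the MOS SF-12, the MPQ, the HADS, the IIEF, and the MSHQ", which again includes no expectation measure. This last point only confirms the list of measures. Sections 10.1, 10.5 and 10.6.1 leave analysis detail to the Data Analysis and Monitoring Plan, so the absence of a described analysis is not counted here.

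**The case against.** The strongest objection is that a measure missing from the protocol text may still be collected. Appendix A is demonstrably not exhaustive: the treatment guess is planned in 8.4 and 10.3 but has no row of its own. Appendix A also gives form titles without items, so the content of the pre-screening, medical history and eligibility forms is not visible. The list in 7.3 covers symptom questionnaires, where an expectation item need not appear. Operational detail is deferred to a Manual of Procedures that is not at hand.

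This stands as a limit on certainty. A reader might infer that none of the 270 planned men would have an expectation value, or that the trial cannot answer objective 4. The documents do not support either statement; they show only that no measure is named. The objection does not remove the point, however. The treatment guess lacks a form row but is described twice in the text, whereas expectation is not described as a data item anywhere. If an item does exist on an unseen form, the protocol should name it.

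A reader might also infer that expectation must be recorded before randomisation. Objective 4 sets no timing, and under blinding a question asked just after allocation but before the first dose could also serve. What does stand is that the answer must precede any treatment effect.

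Finally, a treatment-by-expectation interaction might seem to be required. Objective 4 does not ask for one, and section 10.2 sizes the trial for a 20-point main effect (40% against 60%), not for an interaction.

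**Conclusion.** The point holds in this form: secondary objective 4 has no named measure in the endpoints, the visit procedures or the form schedule, and the end-of-study treatment guess is not a substitute. As written, the protocol provides no data source for one of its four secondary objectives. This is a mismatch between an objective and the planned data collection, so it is not a detail that can be left to an analysis plan.

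The conclusion rests on the protocol text and form titles, and assumes that no unlisted form carries an expectation item. If one does, the point reduces to naming it in the protocol. The primary comparison, the sample size, the interim rule and the safety evaluation do not depend on it. It should be corrected, but it does not threaten the trial's main result.

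**What to change.** Add a named expectation item to the Visit 2 forms in section 7.3 and Appendix A, and list it in section 2.6.2. State that it is completed before study drug is started, and preferably before randomisation. Visit 2 already includes patient questionnaires, so no new visit is needed. Analyse the item as a baseline predictor of symptom severity and of response; label any treatment-by-expectation term exploratory.

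If an item already exists on a form or in the Manual of Procedures, naming it in those three places and stating its timing is enough. If the network does not wish to collect it, the sponsor should delete objective 4 by amendment.

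The cost is one extra question at an existing visit and a form change. Men already randomised would lack the value, so the analysis would cover later entrants only, and the usable number shrinks the longer the change is delayed.
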